5.1 Study objectives

The objectives of the study are as follows (Protocol, Final Version 12, 20.01.2020 Section 3).

Primary objectives

- 1) To obtain preliminary data on whether ketamine is effective in promoting and prolonging abstinence in alcohol dependent patients following detoxification.
- 2) To assess safety and tolerability of ketamine in alcohol dependence.

Secondary objectives

- 1) To make an early assessment on likely compliance to a combined ketamine and relapse prevention based cognitive behavioural therapy (CBT).
- 2) To obtain preliminary data as to whether ketamine alone is as effective as a combined ketamine and psychotherapy treatment.

5.2 Endpoints

The primary and secondary outcome variables are set out in the Protocol, Final Version 12, 20.01.2020, Section 13.1 (reproduced in Table 2). There are two primary outcomes:

- 1) relapse (defined as 5 drinks (8.1 units alcohol) in men and 4 drinks (6.5 units alcohol) in women on a single occasion) at 6-month follow-up; binary outcome; and
- 2) percentage days abstinent (not using alcohol at all) at 6-month follow-up; percentage, to be analysed as a continuous variable.

The two primary outcomes are to be derived from timeline follow-back.

There are 19 secondary variables, derived from 16 secondary outcomes (Protocol, Final Version 12, 20.01.2020, Section 13.1.2; depression is measured by two variables, Beck Depression Inventory and Hamilton Depression Scale; Short Form Health Survey 12 (SF-12) produces a physical and a mental component scale; psychotic symptoms is measured by two variables, Brief Psychiatric Rating Scale and Psychotomimetic States Inventory).

- 1) maximum number of days of continuous abstinence within the first 3 months (time-line follow back); continuous;
- 2) percentage days abstinent at 3 months (time-line follow back); percentage, to be analysed as a continuous outcome;
- 3) Profile of Mood states; continuous;
- 4) Beck Depression Inventory; continuous;
- 5) Hamilton Depression Scale; continuous;
- 6) Speilberger Trait Anxiety Inventory; continuous;
- 7) Brief Psychiatric Rating Scale; continuous;
- 8) Psychotomimetic States Inventory; continuous;
- 9) Fagerstrom Test of Nicotine Dependence (FTND; smokers only); continuous;
- 10) Alcohol craving (visual analogue scale); continuous;
- 11) Alcohol Craving Questionnaire - short-form (ACQ-NOW);
- 12) Short Form Health Survey 12 (SF-12), physical component scale (PCS); continuous;
- 13) Short Form Health Survey 12 (SF-12), mental component scale (MCS); continuous;
- 14) episodic memory (Prose Recall); continuous;
- 15) delay discounting; continuous;
- 16) response inhibition (Stop Signal Reaction time); continuous;
- 17) working memory; continuous;
- 18) hippocampal functioning (Pattern Recognition Test); continuous; and
- 19) adverse effects (visual analogue scale); continuous.

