### 3 Objectives

Primary objectives:

- 1) To obtain preliminary data on whether ketamine is effective in promoting and prolonging abstinence in alcohol dependent patients following detoxification.
- 2) To assess safety and tolerability of ketamine in alcohol dependence

Secondary objectives:

- 1) To make an early assessment on likely compliance to a combined ketamine and relapse prevention based cognitive behavioural therapy (CBT)
- 2) To obtain preliminary data as to whether ketamine alone is as effective as a combined ketamine and psychotherapy treatment.

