### 4 Trial design

#### 4.1 Overall design

[figure not shown]
This non-commercial parallel group, placebo-controlled double blind design aims to make a preliminary assessment of the effectiveness of ketamine in promoting and prolonging abstinence in alcohol dependent patients (Fig. 1). *Why this design was chosen:* A parallel group design is chosen as a crossover would not be feasible with the long time-scales of the study, and given marked carry-over effects that occur in substance-use reduction studies. Three weekly doses of ketamine were chosen as this protocol showed effectiveness in the preliminary studies [33]. This approach has been chosen, rather than a full-scale trial as it is important to confirm the preliminary findings in alcohol dependence. We have chosen to assess outcomes at 3 months and 6 months as from examining other pharmacological and non-pharmacological trials, the largest change in drinking behaviour occurs in the first 3 months and then tails off [40]. However we will follow up again at 6 months to index maintenance of the treatment effect (balancing against the issues of retention of patients in the trial).

For the purpose of this study, Relapse: 5 drinks (drink=13g) in men (8.1units) and 4 drinks (6.5 units) in women on any single occasion and Lapse is defined as 'any other episode of alcohol consumption'.

*Blinding to the IMP:* The trial design will be double blinded. This has been chosen so as to reduce any bias from the power of suggestion of which treatment the patient is received by both the researchers and the patient. The pharmacy or delegated unblinded personnel at both sites will prepare

the syringe for infusion in a blinded fashion so that the administering anaesthetist, psychological researcher and patient are all blind to treatment allocation.

Figure 1: Schematic of overall trial design from recruitment to end of follow up

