- The Alcohol TimeLine Follow Back (TLFB) is a drinking assessment method that obtains estimates of daily drinking and has been evaluated with clinical and nonclinical populations. Using a calendar, people provide retrospective estimates of their daily drinking over a specified time period. Several memory aids can be used to enhance recall (e.g., calendar; key dates serve as anchors for reporting drinking; standard drink conversion). The Alcohol TLFB has been shown to have good psychometric characteristics with a variety of drinker groups, and can generate variables that provide a wide range of information about an individual's drinking (e.g., pattern, variability, and magnitude of drinking).
- A drink diary will be given to each participant to take home in between Visits 8, 9 and 10. Participants will be asked to record their alcohol consumption every day in between study visits. Drink diaries are regularly used in alcohol research to record subjective alcohol consumption.
- Alcohol Craving Questionnaire - short-form (ACQ-NOW) is a 12-item scale that assesses current alcohol craving.

Validated Neurocognitive measures:

- Delay discounting (e.g. monetary choice questionnaire): this is a task that measures an individual's preference for immediate small award over a long term bigger gain.
- Prose recall task: this looks at episodic memory by testing participants recall of a short news broadcast.

- Stop signal task: Stop signal reaction time examines response inhibition, participants have to inhibit prepotent responses to stimuli on the screen when they see a cue or 'stop signal'.
- Working memory task (e.g. digit span WAIS-IV): Working memory measures an individual's ability to maintain and manipulate small amounts of information.
- Pattern recognition memory task (BPS-O Task) is a memory task that taps hippocampal functioning and requires participants to distinguish between perceptually similar items that they have seen before and those they have not.

Questionnaires that are not validated:

- The Pre-Screening questionnaire has been developed to assess suitability for inclusion into the trial.
- Adverse Effects Visual Analogue Scale (VAS) has been developed to measure adverse events during the ketamine infusion and treatment.
- Craving VAS: a one item visual analogue scale will be used to assess craving for alcohol anchored at one end with 'No desire to drink alcohol' and the other 'Very strong desire to drink alcohol'.

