### **13.3.2 Primary outcome analysis**

There are two primary outcomes: (i) proportion relapsed (recommenced using alcohol) at 6-month follow-up; and (ii) percentage of days abstinent at 6-month follow-up (the denominator being 175 days). The proportion of relapsed participants at 6-month follow-up will be reported as a percentage for each arm, as well as for the ketamine arms combined and

the psychotherapy arms combined. Although no formal power calculations for a between-group analysis have been performed, the proportion of relapsed participants at 6-month follow-up will be expressed as a relative risk (RR) with a 95% confidence interval for the following comparisons: (i) all ketamine participants versus all non-ketamine participants; (ii) ketamine + psychotherapy participants versus ketamine + non-psychotherapy participants; and (iii) ketamine + psychotherapy participants vs. placebo + no psychotherapy participants. These analyses are purely exploratory and should be viewed with caution both in the light of lack of power and multiple testing. Percentage of days abstinent at 6-month follow-up will be reported descriptively in the same way by arm and combination of arms; additionally, the between-group mean differences and 95% confidence intervals will be reported for the comparisons set out above; again, these analyses should be regarded as exploratory. The primary analysis will be an intention-to-treat (ITT) complete case analysis including all randomised participants. A secondary analysis will be conducted including only those participants deemed to have completed to a sufficient degree their allocated interventions, that is, a per protocol analysis. All analyses will be performed by a statistician who is blinded to the treatment allocations and will be performed using Stata v.13.

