5.3 Derived variables

The only derived variables will be the binary relapse variable and the number/percentage of days abstinent, to be derived from timeline follow-back data. Further details are to be confirmed.

6 General analysis considerations

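### Relapse is analysed only as a yes/no at 6 months although it is recorded by day, so this outcome cannot separate early from late relapse; a supplementary mean relapse-free time would help

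*SAP*

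**What the plan says.** The first primary objective (Protocol 3, repeated in SAP 5.1) is "To obtain preliminary data on whether ketamine is effective in promoting and prolonging abstinence".

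Both primary outcomes come from timeline follow-back, in which "people provide retrospective estimates of their daily drinking over a specified time period" (Protocol 7.9.1). By the schedule in Appendix B it is taken at every visit from screening to visit 10 except visits 3, 5 and 7.

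- **Relapse** (SAP 5.2) is 5 drinks for men or 4 for women "on a single occasion) at 6-month follow-up; binary outcome". Under Protocol 13.3.2 the proportion of "relapsed participants at 6-month follow-up will be expressed as a relative risk (RR) with a 95% confidence interval", for three comparisons.
- **Percentage of days abstinent** at 6 months is the other primary outcome. Protocol 13.3.2 sets its denominator at 175 days, and mean differences are planned for the same three comparisons.
- **Unbroken abstinence** appears only as a secondary outcome, the "maximum number of days of continuous abstinence within the first 3 months" (SAP 5.2), compared only for ketamine versus placebo (SAP 6.2).

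SAP 5.3 states: "The only derived variables will be the binary relapse variable and the number/percentage of days abstinent". It leaves further details of the derivation to be confirmed. No time to relapse, Kaplan-Meier curve, hazard ratio or restricted mean is planned.

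**The concern.** Prolonging abstinence is a statement about time, and the date of the first qualifying occasion will already be in the data. The relapse outcome discards it. If ketamine postpones relapse and the placebo and ketamine arms have met by month 6, the relative risk is 1 even though participants gained weeks without relapse.

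The other two measures fill the gap only in part. Percentage of days abstinent mixes when drinking starts with how often people drink afterwards. It counts any alcohol rather than relapse, and its primary analysis uses complete cases. The longest run stops at 3 months and gives nothing for the two comparisons that involve psychotherapy, one of which serves the second secondary objective (ketamine alone versus ketamine with psychotherapy).

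Protocol 13.2.1 presents the trial as an early indicator of whether a larger trial is warranted. The cost would be a less informative answer on the part of the objective that concerns duration.

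**Working it through.** **1. The plan's own figure.** With 24 per drug arm after 50% drop-out and relapse of 50% versus 25% (Protocol 13.2.1): SE = √(0.5×0.5/24 + 0.25×0.75/24) = 0.135, and 0.25 ± 1.645×0.135 gives 2.8% to 47.2%. This matches the stated 3% to 47%. The plan makes no tests, so power below (two-sided 5%) is only a yardstick for precision.

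**2. Constant hazard ratio, full follow-up, 48 versus 48.** For 50% versus 25%, HR = ln 0.75/ln 0.5 = 0.415.
- Binary: pooled SE √(2×0.375×0.625/48) = 0.0988, unpooled SE √(0.4375/48) = 0.0955. Power = Φ((0.25 − 1.96×0.0988)/0.0955) = Φ(0.59) = 72%.
- Log-rank: expected events 48×0.5 + 48×0.25 = 36. Power = Φ(√36/2 × |ln 0.415| − 1.96) = Φ(0.68) = 75%.

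For 70% versus 45% (HR = ln 0.55/ln 0.3 = 0.497) the same formulas give 70% and 74%. Simulation puts the gain from dating relapse at 1 and 3 points.

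**3. Simulation, 48 versus 48, 50% drop-out unrelated to relapse.** Entries are the chance (%) that a 95% interval favours ketamine and excludes no effect. All scenarios are assumptions except the relapse rates of 50% versus 25% in A (Protocol 13.2.1) and the placebo rates of 50% at 3 months and 70% at 6 in B, C and the delay (Protocol 2.1). Ranges for days abstinent come from assuming that 30% to 85% of days after relapse are abstinent; other ranges are spread between runs.

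| Scenario, placebo versus ketamine | Binary, completers | Kaplan-Meier risk at 6 months | Log-rank | Mean relapse-free time to day 161 | Days abstinent, completers |
|---|---|---|---|---|---|
| A: 50% v 25% at 6 months, constant effect | 45 | 59 | 60 | 55 | 19–33 |
| B: 70% v 45% at 6 months, constant effect | 43 | 56 | 62 | 59 | not run |
| C: 50% v 25% at 3 months, equal hazards after (70% v 55% at 6) | 19 | 25 | 50 | 62–63 | 14–37 |
| Pure delay: 50% v 25% at 3 months, 70% v 70% at 6 | 2–4 | not run | 14–24 | 43 | 9–21 |

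In A and B most of the gain over the binary outcome is already in the Kaplan-Meier column (59 − 45 = 14 of 15 points; 56 − 43 = 13 of 19 as rounded, about 20 before rounding). It comes from using partial follow-up rather than from the time scale.

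**4. The same with full follow-up.** Binary, log-rank and mean relapse-free time give 73, 74 and 61 in A; 71, 74 and 66 in B; 33, 52 and 70 in C. In C, days abstinent gives 40–61. For the pure delay, two-sided, binary gives about 5, log-rank 15, mean relapse-free time (to day 175) 42, days abstinent 14–33, and the planned 3-month run 63–66.

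**5. Size of a pure delay in days** (3 months = 84 days, 6 months = 175). The area under each curve is the drop in survival divided by the hazard, by segment.
- Placebo: 0.5/(ln 2/84) + 0.2/(ln(0.5/0.3)/91) = 60.6 + 35.6 = 96.2 days.
- Ketamine: 0.25/(ln(1/0.75)/84) + 0.45/(ln(0.75/0.3)/91) = 73.0 + 44.7 = 117.7 days.
- Gain: 21.5 days, with a risk difference at 6 months of 0. The simulated 95% half-width with full follow-up is 24 days at 48 versus 48 and 34 days at 24 versus 24.

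**6. Why days abstinent is indirect.** If a fraction q of days after relapse is abstinent, the mean percentage is q + (1 − q)t/175. The 21.5-day gain becomes (1 − q)×21.5/175, that is 1.8 points at q = 0.85 and 8.6 at q = 0.30. If everyone shared one q, this outcome would carry almost the same information as relapse-free time under full follow-up. It loses ground when q varies between people and when complete-case analysis drops half the sample.

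**The case against.** The strongest reply is that the plan already measures duration. Percentage of days abstinent is a primary outcome, covers the whole follow-up and rises when drinking starts later; the 3-month run does best of all for a pure delay (63–66%). This stands. A reader might infer that the plan has no estimate of duration, or that a treatment which delays relapse would be missed altogether. The documents do not support either reading.

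Other replies also carry weight:

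- Protocol 4.1 chooses 6 months in order to see whether the effect is maintained, so a late relapse endpoint is deliberate. Its remark that "the largest change in drinking behaviour occurs in the first 3 months and then tails off" describes other trials. It does not say that ketamine's hazard ratio becomes 1 after month 3, so scenario C and the pure delay are possibilities and not predictions.
- Most of the gain in A and B is a missing-data gain. SAP 6.5 plans multiple imputation for the primary outcomes when more than 5% are missing, which the simulation omits, and the protocol regards 50% drop-out as very cautious.
- Drinking is known only up to the last attended assessment. Censoring there cut log-rank power from 58% to 54% in A and from 63% to 57% in B.
- For a constant effect with full follow-up, mean relapse-free time is less powerful than the binary outcome (61 versus 73 in A), and the log-rank test is weak for a pure delay.

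These replies argue for keeping the binary outcome and against making a hazard ratio the main addition. They do not supply a relapse-free time over 6 months. That all inference is exploratory and without p-values limits the weight of any single estimate, but interval width still matters.

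**Conclusion.** The point holds for the relapse outcome and not for the plan as a whole. Relapse as planned does not distinguish early from late and largely misses a delay that has caught up by month 6. The plan's other outcomes see such a delay indirectly, or directly but only to 3 months and for one comparison.

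The gain from dating relapse is 1 to 3 points for a constant effect with full follow-up and about 15 to 20 points at 50% drop-out, the latter mainly from partial follow-up. For an early or purely delaying effect at that drop-out, mean relapse-free time is clearly more informative than either primary outcome. With full follow-up its lead over days abstinent narrows and depends on how people drink after relapse. Even at 48 versus 48, a 21-day gain would carry an interval of about ± 24 days.

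The figures assume drop-out unrelated to relapse, first drink and relapse starting together, and relapse meaning any qualifying occasion by 6 months. The last is not settled: Protocol 13.3.2 glosses relapse as resuming alcohol use. This is a supplementary improvement worth considering, not a defect that invalidates the planned analysis.

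**What to change.** Keep the binary relapse and its relative risk.

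- **SAP 5.3:** add days from visit 2 to the first occasion meeting the 5/4-drink definition, censored at the last day covered by timeline follow-back, that is the last attended assessment.
- **SAP 4.5 and 6.2:** as a supplementary exploratory analysis for the same three comparisons, report Kaplan-Meier curves and the site-adjusted difference in mean relapse-free days to day 161 (23×7, the earliest visit 10) with a 95% interval. Name this as the estimate for prolonging abstinence. Pseudo-value regression on arm and site would avoid fitting a curve in each small site stratum. A hazard ratio can be given as optional description.

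The cost is SAP wording, one derived variable, one table and one figure, with no new data, visits or participants. The downsides are one more exploratory estimate per comparison, and relapse dates recalled over about 12 weeks between visits 9 and 10 (10 to 14 by the visit windows). Censoring also assumes that drop-out is unrelated to later relapse, which is no stronger than what the complete-case analysis assumes.

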5.3 Derived variables

The only derived variables will be the binary relapse variable and the number/percentage of days abstinent, to be derived from timeline follow-back data. Further details are to be confirmed.

6 General analysis considerations

6.1 Timing of analyses

An analysis of loss to follow-up only (using count data only) for the ketamine arms will be performed at 3-month follow-up. The trial will be discontinued if more than 42/48 (88%) participants allocated to ketamine are lost to follow-up at 3 months. No further interim analyses are planned (confirmed by funder, December 2019).

The final analyses will take place once all outcome data (after 6-month follow-up is complete) has been entered into the trial database and cleaned. The data manager will liaise with the trial statistician to make the outcome data available for analysis.

Table 2 Outcome variables

Outcome	Variable type	Timepoints measured	Data source/measurement method
Primary outcomes			
Relapse (defined as 5 drinks (8.1 units alcohol) in men and 4 drinks (6.5 units alcohol) in women on a single occasion)	Binary	6 months	Timeline follow-back (participant report)
Percentage days abstinent (not using alcohol at all)	Percentage	6 months	Timeline follow-back (participant report)
Secondary outcomes			
Number of days of continuous abstinence	Continuous	3 months	Timeline follow-back (participant report)
Percentage days abstinent	Continuous	3 months	SCRAM-X Timeline follow-back (participant report)
Profile of Mood states;	Continuous	6 months	Questionnaire: participant report
Beck Depression Inventory	Continuous	6 months	Questionnaire: participant report
Hamilton Depression Scale	Continuous	6 months	Questionnaire: participant report
Speilberger Trait Anxiety Inventory	Continuous	6 months	Questionnaire: participant report
Brief Psychiatric Rating Scale	Continuous	6 months	Questionnaire: participant report
Psychotomimetic States Inventory	Continuous	6 months	Questionnaire: participant report
Fagerstrom Test of Nicotine Dependence (FTND)	Continuous	6 months	Questionnaire: participant report
Alcohol Craving (visual analogue scale)	Continuous	6 months	Questionnaire: participant report
Alcohol Craving Questionnaire (ACQ);	Continuous	6 months	Questionnaire: participant report
Short Form Health Survey 12 (SF-12),	Continuous	6 months	Questionnaire: participant report

physical component scale (PCS)			
Short Form Health Survey 12 (SF-12), mental component scale (MCS)	Continuous	6 months	Questionnaire: participant report
Episodic memory (Prose Recall)	Continuous	6 months	Computer task: participant completed
Delay discounting	Continuous	6 months	Questionnaire: participant report
Response inhibition (Stop Signal Reaction time)	Continuous	6 months	Computer task: participant completed
Working memory	Continuous	6 months	Questionnaire: participant report
Hippocampal functioning (Pattern Recognition Test)	Continuous	6 months	Computer task: participant completed
Adverse effects (visual analogue scale)	Continuous	6 months	Questionnaire: participant report

